7. *Successful control of inflammation with complete discontinuation of steroids (Phase I 6-12 months).* Some individuals may be able to taper completely off of steroids while maintaining control of inflammation. The outcome variable is the fraction of individuals achieving such control in both eyes (out of the number of individuals starting therapy). We propose to compare this fraction between the two treatment groups using logistic regression. The statistical analysis will otherwise be identical to the primary analysis.

8. *Macular edema.* We wish to compare the fraction of patients with macular edema at 6 months, between the two treatment arms. This will be conducted using the Fisher exact test, with a two-sided test at alpha of 0.05. Supplementary analyses will be based on logistic regression using the presence of macular edema as a binary outcome variable, with regressors ("independent variables") of treatment arm and anatomic location. Further analyses (including other baseline covariates or other subsets) will be labeled as exploratory.

9. *Change in Macular thickness.* We propose to test the hypothesis that macular thickness is different in the two treatment arms, at 6 months. We propose to model the macular thickness at 6 months using two regressors: treatment arm and baseline thickness. We will test the hypothesis that treatment arm is associated with final macular thickness, using the T-test of the regression coefficient for treatment arm in the model including baseline thickness as a second covariate (two sided using $\alpha=0.05$). We will examine residuals for normality and homoskedasticity, and prepare residual vs fitted value plots. Standard transformations will be used in case of evidence that the assumptions have been violated.

We will also look at change in macular thickness in only patients who had macular edema at Baseline.

10. *Bayesian analysis.* Prior to data collection, we will elicit a Bayesian prior for the effect size (difference between the two treatment arms) from a group of uveitis experts, using methods our group has previously applied to the [REDACTED]. The likelihood

function corresponding to Equation (1) will be used to yield a posterior distribution for the effect size. Quantiles of this distribution will be reported, together with sensitivity analyses (with respect to model choice, influential observations, and prior distribution).

11. *Alternative definitions for success.* Other definitions will be examined: (i) changing the algorithm for assigning values for unobservable uveitis examination fields (anterior cells, vitreous haze, retinal/choroidal lesions) so that any worsening of ability to assess the eye for any reason is scored a failure, or (ii) use of vitreous cells in the definition of uveitis.

12. *Change in vitreous haze* will be assessed using clustered polytomous logistic regression, using baseline vitreous haze as a covariate and follow-up time. Vitreous haze is an ordinal outcome variable. A random effect is needed because the two eyes of a given patient cannot be treated as statistically independent. Both the NEI and Davis scales will be analyzed, for both direct observations and photographic grading. Treatment assignment will be a covariate. Alternative methods will be examined, including a simple McNemar test in which we dichotomize vitreous haze assessments at baseline and at the final observation.

13. *Rate of adverse events* and the proportion of patients discontinuing due to adverse events will be tabulated by treatment assignment, age, and gender; confidence intervals will be reported.

14. *Treatment efficacy in VKH patients* will be assessed as a planned subgroup analysis. Note that anatomic location is also a planned subgroup analysis, as well as study site and study country (aggregating all sites within each country).

15. *Dose reduction* will be compared by arm using logistic regression based on treatment, and other covariates as needed.

16. If no difference is found for the primary outcome comparing treatment success between arms, we will assess whether methotrexate is non-inferior to mycophenolate mofetil, assuming a 10% non-inferiority margin. The non-inferiority margin of 10% is clinically meaningful and was based on investigator consensus. Methotrexate will be considered non-inferior to mycophenolate if the lower limit of the 95% CI for treatment success at 6 months is less than 10%. This analysis will be conducted because mycophenolate mofetil is much more expensive than methotrexate, so a determination that methotrexate is not inferior has clinical implications. We are interested in a one-sided comparison given the cost differential between methotrexate and mycophenolate mofetil.

17. Additional exploratory modeling will be conducted using clustered multinomial logistic regression using all time points and all observations of anterior chamber cells, vitreous haze, and retinal/choroidal lesions.

3.2.3 Specific Aim 2

Primary Analysis.

The primary analysis will compare the proportion of successes between (a) patients treated with mycophenolate mofetil following failure on methotrexate and (b) patients treated with methotrexate following failure on mycophenolate mofetil.

Specifically, we will conduct a logistic regression in which success or failure will be the outcome, and the predictors (regressors, independent variables) will be treatment group and reason for failure of the first drug (lack of efficacy vs any other reason). Supplementary analyses will include anatomic location (intermediate vs posterior/pan) and country. We will test the hypothesis that the coefficient for treatment group equals zero (i.e., that mycophenolate mofetil rescue after methotrexate failure has the same result as methotrexate rescue after mycophenolate mofetil failure). All alpha levels will be two-sided.

It is important to emphasize that estimation of the success rate of the second drug following the failure of the first is a central goal of the trial, arguably as or more important than the hypothesis test itself. The success rates and confidence intervals will be presented regardless of the results of the hypothesis test.

Secondary Analyses.

The following secondary analyses are planned.

We will also present the estimated success proportion in both treatment groups, together with the 95% confidence intervals. The two groups are the individuals who were undergoing methotrexate rescue therapy after mycophenolate mofetil, and those who were undergoing mycophenolate mofetil rescue therapy after methotrexate. Logistic regression will also be used to adjust for study site.

The second prespecified analysis will compare the rate of success between rescue patients and first-line patients, using logistic regression; we will test the hypothesis that the coefficient for rescue/initial equals zero. A supplemental variation of this analysis will include an additional predictor for whether the patient was on rescue therapy due to lack of efficacy, lack of safety or intolerance, or anatomic location. Two separate analyses are planned, each with an alpha of 0.05.

Exploratory and descriptive analyses of covariates such as reason for failure of the initial regime, age, disease (e.g., VKH), and affected region of the eye, will be presented.

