*Every monthly visit scheduled will be calculated from the baseline visit date (Phase 1), using the average amount of days per month. If a patient does not come in within the visit window, every attempt should be made to get them in for a clinic visit as soon as possible.

Table 10: Visit Schedule Phase I (6-12 months)

Visit	Window (Weeks)
Month 9*	±15 days
Month 12*	-15 to +30

* Since baseline/treatment administration (Phase 1)

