4.4. Follow-up visits

It is strongly encouraged for all follow up data to be collected within the study visit window, but should be collected regardless.

All Phase II procedures and protocol are the same as Phase I. For Phase I patients who are continuing on the same medication, physicians can see the patients as often as they would like. However, for purposes of this study we will only be recording information at Month 9 and Month 12, or a non-study visit that leads to treatment failure.

Laboratory test results will be collected monthly.

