- Baseline best spectacle-corrected visual acuity, vitreous haze, macular thickness
- Vasculitis

Inclusion of Data

- Data will be included for all outcomes within the window period of -2 weeks to +4 weeks around the 6 Month Visit date for Phase I (0-6 months).
- Data will be included for all outcomes within the window period of -2 weeks to +4 weeks around the 12 Month Visit date for Phase I (6-12 months).
- Data will be included for all outcomes within the window period of -2 weeks to +4 weeks around the 6 Month Visit for Phase II (0-6 months).

3.2.2 Specific Aim 1

Primary Analysis.

The primary analysis will be a logistic regression model, predicting treatment success at 6 months based on treatment arm. We wish to aggregate sites within countries, and countries within treatments provided we find no evidence of heterogeneity of sites or countries.

Specifically, the pre-specified primary analysis will be performed as follows. We denote the assignment group of patient i , $i=1, \dots, N$ (where N is the number of subjects) by X_p^1 which equals 0 when the patient is in the methotrexate group and 1 when the patient is in the mycophenolate mofetil group. The outcome variable is Y_p which is 1 if treatment success of patient i is achieved by six months, and 0 otherwise. The variable is missing if the patient is lost to follow-up or drops out of the study for reasons other than discontinuation due to intolerance or adverse events; if the patient discontinues the medication due to intolerance or adverse events such as abnormal laboratory findings, the value is 0.

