3.5 Missing data and loss to follow-up

Values of the primary study endpoint (treatment success at six months) cannot be analyzed when the individual is lost to follow-up. We distinguish information which is missing because of possible progression of the underlying condition we wish to treat from information which is lost for some other reason. Earlier, we discussed methods for handling missing values for specific

uveitis fields in individuals. The discussion in this section applies only to loss to follow-up or to dropping out of the study. As emphasized in Carpenter & Kenward (2007), “there can be no universal analysis when data are missing”. Our purpose is to vary the assumptions as well as the methods, to establish that the estimates of the treatment effect are robust as such assumptions are varied.

Our priority is the preservation of the intent to treat principle. We propose to report the results from all of the following methods:

1. The use of regression-based multiple imputation, based on all observed data for the patient.
2. Use of longitudinal generalized linear mixed effects regression, with visit as a covariate, and including a random effect for each person and for each eye within each person, using all the available measurements on each individual
3. Sensitivity analysis in which missing final outcome values are assigned success or failure, and the analysis conducted conditional on these assignments.
4. Analysis of complete cases only (individuals for which the six month follow-up is available)

However, we are proposing that **method 4 (complete case analysis) be considered the primary outcome**, based on recommendation by the DSMB. All other analyses are to be considered supplementary.

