4.2 Major protocol deviations

The incidence of deviations from the inclusion and exclusion criteria will be summarized using counts and percentages, and the treatment groups compared for the overall frequency of deviations using a $2 \times N$ Fisher's exact test. Similar deviations will be grouped into general categories of deviations for a more condensed summary. A listing of deviations by participant will also be produced. Any major deviations from the protocol will be listed and/or summarized, including, but not limited to, participants who:

- never received study drug
- were subsequently found to be ineligible for the study
- never returned for a follow-up visit
- have follow-up visits outside the prescribed visit window
- received a corticosteroid injection >90 days after enrollment for macular edema or at any time for inflammation

The number and percentage of randomized participants actually receiving study medication, permanently discontinuing study drug (subdivided by reason), and receiving injections >90 days past enrollment will be summarized. A summary of study participants randomized by site will also be provided. Treatment groups will be compared for the proportion and reason for study drug discontinuation using the chi-square test. A summary of participant status at the end of the study period will also be generated with categories including lost to follow-up.

5 Data Collection and Quality Assurance

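### The SAP's data-inclusion windows are three days narrower than the protocol's visit windows, and the SAP contradicts itself on whether month-6 visits on those days enter the complete-case primary analysis

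*Combined protocol and SAP*

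**What the plan says.** **Protocol.** Table 9 (section 4.1.1) gives the month-6 visit, in Phase I and in Phase II, a window of -15 to +30. Table 10 gives the same for month 12. Table 10's column is headed in weeks, but the neighbouring entries in both tables are in days, and Table 1 speaks of a one-month visit window, so days are clearly meant. The target date is set as follows: "Every monthly visit scheduled will be calculated from the baseline visit date (Phase 1), using the average amount of days per month". On timing, section 4.4 says: "It is strongly encouraged for all follow up data to be collected within the study visit window, but should be collected regardless".

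**SAP, inclusion rule.** Section 3.2.1, under Inclusion of Data, says: "Data will be included for all outcomes within the window period of -2 weeks to +4 weeks around the 6 Month Visit date". I take the visit date there to be the scheduled target date. Two parallel sentences apply the same limits to month 12 and to Phase II month 6.

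**SAP, missing outcomes.** Section 3.2.2 says of the primary outcome: "The variable is missing if the patient is lost to follow-up or drops out of the study", apart from stopping for intolerance or adverse events. For those patients, "if the patient discontinues the medication due to intolerance or adverse events such as abnormal laboratory findings, the value is 0". Section 3.5 describes its fourth method as "Analysis of complete cases only (individuals for which the six month follow-up is available", and proposes that "method 4 (complete case analysis) be considered the primary outcome".

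**SAP, off-window visits.** Section 4.2 lists among major protocol deviations participants who "have follow-up visits outside the prescribed visit window". Section 4.1 removes major deviations from the per-protocol population only. The intent-to-treat population remains primary for efficacy.

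**The concern.** Sites work to the protocol window, and the analyst works to the SAP window. A patient seen on day +29 has complied with the protocol but falls outside the only SAP sentence that says which visit dates count as month-6 data. That sentence covers all outcomes, so it reaches the primary one.

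A complete-case primary analysis depends on a clear rule for who is a complete case. Here two parts of the SAP give different answers for the same patient. If the rule stays open, someone has to settle it after data have accrued. SAP 3.10 and 3.10.2 have the principal statistician run the interim analyses unmasked, on the primary outcome and with the final-analysis model. Membership of the primary set should be fixed before then. The sample size also leaves no slack: it gives about 80% power after 10% loss to follow-up.

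**Working it through.** **1. Reproduce the planned size.** Inputs from SAP 3.4.1: success 0.4 versus 0.6, two-sided alpha 0.05, 80% power, 10% loss. Equation (5):

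4 × (1.960 + 0.842)² × 0.5 × 0.5 / 0.2² = 196.2 in total.

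Allowing for loss, 196.2 × 1.10 = 215.8 or 196.2 / 0.90 = 218.0. The stated 216 is reproduced. Planned evaluable patients: 216 × 0.9 = 194.4, or 97.2 per arm.

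**2. Compare the windows.**
- Protocol: 15 + 1 + 30 = 46 calendar days.
- SAP: 14 + 1 + 28 = 43 calendar days.
- In the protocol window only: days -15, +29 and +30.

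Taking an average month as 365.25 / 12 = 30.44 days, the month-6 target is about day 182.6. The protocol window then runs from about day 167.6 to 212.6, and the SAP window from about day 168.6 to 210.6.

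**3. Follow a visit on day +29 through the SAP.**

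| SAP text | Status of the visit |
|---|---|
| 3.2.1, inclusion window | Outside, so not included |
| 3.2.2, missing outcome | Not missing: neither lost to follow-up nor dropped out |
| 3.5, complete case | Six-month follow-up is available; no window stated |
| 4.2 with 4.1 | A deviation only if the prescribed window means the SAP's; then out of the per-protocol set, still in intent-to-treat |

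The first row conflicts with the second and third. The fourth does not say which window it means.

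**4. Size if such visits were left out.** With n per arm, the two-proportion power is

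Φ{[0.2√n - 1.960 × √(2 × 0.25)] / √(0.24 + 0.24)}.

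At n = 97.2: (1.972 - 1.386) / 0.693 = 0.846, so power is 80.1%. The share affected is an assumption.

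| Share affected | Patients lost (of 194.4) | n per arm | Power |
|---|---|---|---|
| 0% | 0 | 97.2 | 80.1% |
| 1% | 1.9 | 96.2 | 79.7% |
| 2% | 3.9 | 95.3 | 79.3% |
| 3% | 5.8 | 94.3 | 78.9% |
| 5% | 9.7 | 92.3 | 78.0% |

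Solving Equation (5) for power instead starts at 79.6% and gives almost the same falls (79.2% at 1%, 77.6% at 5%). Both sets overstate the loss: a patient already scored a failure before month 6 does not depend on the date of that visit.

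**5. A related loose end.** SAP 2.3.2 and 3.1 describe visits every 4 weeks, while the protocol counts average months. A sixth visit booked at 24 weeks (day 168) would fall 168 - 182.6 = -14.6 days from target: inside -15, outside -14, and sensitive to how the target is rounded.

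**The case against.** The best defence is that nothing in the SAP orders these visits to be dropped. Its definitions of a missing outcome and of a complete case carry no window, protocol 2.5.3 says that even missing a visit is not dropping out, and off-window visits are handled as deviations that affect only the per-protocol set. The mismatch also looks like rounding, with half a month and one month written as 15 and 30 days in one document and as 2 and 4 weeks in the other. Most of this stands. It rules out reading the SAP as clearly discarding the visits. It does not remove the inclusion sentence, which covers all outcomes and has no stated consequence for data outside it.

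Three stronger readings are tempting, and the documents support none of them:
- **Compliant patients become missing in the primary analysis.** This follows from one sentence of the SAP only, and the definitions in 3.2.2 and 3.5 point the other way.
- **Power falls to about 77%.** That needs visits spread evenly over the window: 3 / 46 = 6.5%, or 12.7 patients, and 77.4% power. Visits are booked to a target date, and no document suggests an even spread.
- **Late attenders differ from the rest, so the estimate is biased.** This may be so, but it is not shown. One of the three days is early, and nothing suggests that timing differs by arm.

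If some outcomes were set to missing, SAP 3.5 already plans multiple imputation, longitudinal mixed models and assigned success or failure, and 3.3.1 asks how large an effect among the lost patients would change the result.

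**Conclusion.** The point holds as an inconsistency. The SAP window is narrower than the protocol window by one day early and two days late at month 6, month 12 and Phase II month 6. For patients seen on those days at month 6 of Phase I, the SAP's own clauses disagree on whether they belong in the primary analysis.

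The likely effect is small: about 0.4 to 2 points of power if 1% to 5% of evaluable patients were affected and were in fact left out. Both conditions are assumptions, since no distribution of visit dates is given and exclusion is only one reading. No direction of bias can be claimed. The wider gap is that the SAP does not say how a month-6 visit outside either window is scored, although the protocol requires those data to be collected.

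**What to change.** In SAP 3.2.1, replace the window in weeks with the protocol window in days, -15 to +30, at all three endpoints. State the target date and its rounding, in line with the protocol's average-month rule, and reconcile the 4-week visit wording with it. In 3.2.2 or 3.5, state how a month-6 visit outside that window is scored in the complete-case primary analysis, and in 4.2 say which window is meant. Make these changes before any further analysis by arm.

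The cost is SAP wording, with no change to visits or data collection. With the windows aligned, no visit made within the protocol window falls outside the analysis window, and the planned 194.4 evaluable patients and about 80% power are unaffected by this issue.
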